4. Place cryovials into biohazard bag and immediately freeze at -70 to -90°C.
5. Store frozen plasma until ready for testing.

IX. **Assessment of Safety, Dose Modifications and Dose Delays**

- A. This study will be reviewed by the Medical College of Wisconsin Cancer Center Data Safety Monitoring Committee (MCW CC DSMC). A summary of the MCW CC DSMC activities are as follows:
 - i. Review the clinical trial for data integrity and safety.

- ii. Review all unexpected grade 3, and all grade 4, and 5 adverse events, as well as any others requiring expedited reporting as defined in this protocol. (Grades 4 & 5 events must be reported to the DSMC within 5 calendar days of study staff's knowledge.) Review all DSM reports.
- iii. Sequential boundaries will be used to monitor the post-operative wound-complication rate. The accrual will be halted if excessive numbers of grade 3 or 4 (page 32) complications are seen, that is, if the number of complications is equal to or exceeds X out of N patients (X/N) with full follow-up (see below). This is a Pocock-type stopping boundary (Ivanova, et al. 2013) that yields the probability of crossing the boundary at most 5% when the complications rate is equal to 50% (O'Sullivan, et al. 2002).
- iv. Accrual will halt for protocol review if 6/6 (6 patients out of the first 6), then 7/7, 8/8, 9/10, 10/11, 11/13, 12/14, 13/16, 14/18, 15/19, 16/21, 17/22, 18/24, 19/26, 20/27, 21/29, 22/31, 23/32, 24/34, and 25/35 grade 3-4 treatment related AE's.
- v. Submit a summary of any recommendations related to study conduct.
- vi. Terminate the study if deemed unsafe for patients.
- B. A copy of the MCW Cancer Center Data and Safety Monitoring Plan and membership roster will be maintained in the study research file and updated as membership changes.
- C. The committee will review reports from the study PI twice annually (or more frequently if needed) and provide recommendations on trial continuation, suspension or termination as necessary.

X. **Subject Withdrawal Criteria**

- A. This Protocol is designed for 35 patients. Accrual will terminate early based on toxicity analysis. Patients may also withdraw at any point if they wish to not be on study.
- B. Criteria for early Closure

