 - i. Greater than 2 patients who have any grade 4 or higher toxicity during radiation. If a patient has a grade 4 or higher toxicity, then they will be taken off the study, administered a lower dose per fraction per the treating physician, and the study will be closed. We do expect grade 3 skin toxicity (moist desquamation in areas other than skin folds), as many patients have tumors that extend to the surface of the skin and thus will need to be bloused to get the appropriate dose to these areas. Thus, moist desquamation often occurs.
 - ii. ≥60% of patients with post-operative wound complications.
 - iii. As mentioned above, patients may also withdraw at any point if they wish to not be on study.
- C. The research coordinator and PI will be notified of the withdrawal of a patient and the appropriate documentation will be made.
 - i. The IRB will be notified at the time of withdrawal.
- D. Subjects will not be replaced.
- E. Follow up and data collection for withdrawn subjects will terminate at the time of withdrawal.
- F. Dose Modification
 - i. If any grade 4 toxicity occurs, the dose will be modified based on the BED calculator above and the study will be closed.

XI. **Endpoint Assessment**

- A. Study Design:
 - i. This is a non-randomized Phase II pilot protocol to determine the feasibility, toxicity, and disease control (local control, overall and progression-free survival) using hypofractionated pre-operative radiation therapy in patients with primary localized STS.
- B. Primary Endpoint:

- i. The primary aim of this study is to assess local control. We expect local recurrence rates of <7%. Local and regional recurrence will be defined for each lesion per the treating physician(s). Local recurrence will be defined if the patient has evidence of disease on imaging (MRI or CT or PET CT) or physical exam.

C. Secondary Endpoint:

- i. The secondary objective of this study is to assess quality of life, toxicity (see iii), disease-free survival and overall survival. Disease-free survival is defined as the time from enrollment until documented disease-recurrence or death, whichever occurs first. Patients who are disease-free and alive at the time of analysis will be censored at the time of their last follow-up. Patients will be followed for disease-free survival for a minimum of 2 years.
- ii. Quality of life will be assessed via the FACT-L forms and given at the specified time points above.

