- A. The primary aim of a 2-year local recurrence rate of less than 3% will be evaluated by a one-sided equivalence test with an equivalence limit of 5% and a type I error rate of 10%. The study will conclude equivalence if the 2-year cumulative incidence of recurrence is less than 12% at the 0.10 type I error level. Power calculations are based on exact binomial probability calculations with an equivalence determined by no more than 12% local recurrence rate (within 5% of 7%), assuming a true 2-year local recurrence rate of 2.5%.
- B. If the true local recurrence rate is 12%, then with 35 patients the probability of observing a recurrence rate of 3.1% or less (≤ 1 of 35) is 8.97% (one-sided type I error = 0.0897).
- C. If the true local recurrence rate is 2.5%, then with 35 patients the probability of observing recurrence of 3.1% or less (≤ 1 out of 35) is 81.0% (Power).
- D. This is as close as we can get to a one-sided equivalence test with 10% type I error and 80% power with exact binomial calculations. The probability of falsely rejecting the null hypothesis (*hypofractionation treatment is worse than standard*) with only 0 or 1 recurrence out of 35 patients is less than 10% if the actual recurrence rate is 12% or more. There will be at least 80% power to reject this hypothesis if the true recurrence is 2.5% or less.

XIV. Considerations for Toxicity, QOL, Disease-Free Survival and Overall Survival (Secondary Endpoints)

- A. Overall survival and disease-free survival will be estimated using the product limit estimator and presented as Kaplan-Meier plots. Cumulative incidence rates will be calculated for local recurrence and adverse events. Quality of life data will be summarized for each time point, and compared using non-parametric statistical methods.
- B. Toxicity will be measured via the CTCAE v. 4.0 and the MSTS score. We will compare toxicity to the standard historical control for preoperative radiation therapy in STS (NCIC, O'Sullivan et. al) (5)
- C. Quality of Life will be measured with the FACT-L validated questionnaire.

XV. References

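### The power statement for the primary endpoint names 35 patients but gives the results for 32; with 35, power is 78.2%, not 81.0%

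*Combined protocol and SAP*

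**What the plan says.** Section XIII.A bases the power calculation on exact binomial probabilities. The unacceptable 2-year local recurrence rate is 12%, described as "equivalence determined by no more than 12% local recurrence rate (within 5% of 7"%). The assumed true rate is 2.5%, and the test is one-sided at 10%.

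XIII.B says that, at a true rate of 12% and with 35 patients, "the probability of observing a recurrence rate of 3.1% or less (≤ 1 of 35) is 8.97"%. XIII.C says that, at a true rate of 2.5%, "with 35 patients the probability of observing recurrence of 3.1% or less (≤ 1 out of 35) is 81.0% (Power").

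XIII.D draws two conclusions: "This is as close as we can get to a one-sided equivalence test with 10% type I error and 80% power" using exact binomial calculations, and "There will be at least 80% power to reject this hypothesis if the true recurrence is 2.5% or less".

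Section X.A confirms the size: "This Protocol is designed for 35 patients". X.D adds "Subjects will not be replaced", and X.E "Follow up and data collection for withdrawn subjects will terminate at the time of withdrawal".

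**The concern.** The first sign of trouble is the cut-off. One recurrence in 35 is 2.9%, which cannot round to 3.1%. If the percentage belongs to a different denominator, the type I error and power beside it may do so too.

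These are the operating characteristics of the only primary-endpoint test. Anyone approving the protocol is told that 35 patients deliver at least 80% power at the planning rate. The rule also turns on a single event, so its error rates move noticeably with each patient added to or lost from the denominator.

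**Working it through.** **Inputs.** Null rate 12%, true rate 2.5%, one-sided 10% level and exact binomial method (XIII.A); success if at most 1 recurrence, 35 patients (XIII.B to D, X.A).

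**Formula.** With X recurrences among n patients and true rate p:

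P(X ≤ 1) = (1 − p)^n + n·p·(1 − p)^(n−1)

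At p = 0.12 this is the type I error; at p = 0.025 it is the power.

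**Reproducing the plan's figures: n = 32.**
- Cut-off: 1/32 = 3.125%, stated as 3.1%.
- Type I error: 0.88^32 + 32 × 0.12 × 0.88^31 = 0.0167 + 0.0730 = 0.0897, stated as 8.97%.
- Power: 0.975^32 + 32 × 0.025 × 0.975^31 = 0.4448 + 0.3650 = 0.8097, stated as 81.0%.

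All three match. Of the sample sizes from 28 to 40, only 32 gives 0.0897.

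**The size the plan names: n = 35.**
- Cut-off: 1/35 = 2.86%.
- Type I error: 0.88^35 + 35 × 0.12 × 0.88^34 = 0.0114 + 0.0544 = 0.0658.
- Power: 0.975^35 + 35 × 0.025 × 0.975^34 = 0.4122 + 0.3700 = 0.7822.

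None of the three matches the text. Approximations at n = 35 do not rescue it either (type I error / power): Poisson 7.8% / 78.2%; normal with continuity correction 8.0% / 75.1%; normal without correction 4.8% / 55.4%.

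**Neighbouring sample sizes, rule of at most 1 recurrence.**

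| n | Type I error at 12% | Power at 2.5% |
|---|---|---|
| 30 | 11.0% | 82.8% |
| 31 | 9.9% | 81.9% |
| 32 | 9.0% | 81.0% |
| 33 | 8.1% | 80.1% |
| 34 | 7.3% | 79.1% |
| 35 | 6.6% | 78.2% |

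For this rule, only n = 31, 32 and 33 meet both targets (type I error at most 10%, power at least 80%).

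**Could another rule at n = 35 be meant?** Allowing 2 recurrences gives a type I error of 19.2% and power of 94.3%, so no. At most 1 is the largest cut-off that keeps the error below 10%.

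**Where would 80% hold at n = 35?** Power is 80.8% at a true rate of 2.3% and 79.5% at 2.4%; it crosses 80% at about 2.36%.

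**The case against.** The strongest reply is that little turns on this. The shortfall is 1.8 points against the 80% target in a single-arm pilot. The type I error is overstated, so protection against a false claim of equivalence is better than advertised. Neither the rule nor the enrolment has to change. All of that stands, and it limits the weight of the point without making the stated power correct.

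A second reply is that 32 evaluable patients may have been inflated to 35, a loss of 3/35 = 8.6%. That is plausible but only an assumption: the plan mentions no evaluable number and no loss allowance. It would not rescue the text either, because XIII writes the rule consistently as a count out of 35. The written denominator is therefore 35, and the case for 32 rests only on the numerical match.

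A third reply concerns missing 2-year status. The plan schedules MRI every 4 months for two years (section VII) and refers to cumulative incidence (XIII.A, XIV.A), which can accommodate censoring. This is fair, and missing follow-up is secondary here. But the quoted error rates come from a simple count, which needs known status for each patient counted. The plan does not say so, although it neither replaces patients nor follows them after withdrawal.

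**Conclusion.** The point holds. XIII.B to D attribute to 35 patients three figures that belong to 32. For 35 patients the cut-off is 2.9% rather than 3.1%. The type I error is 6.6% rather than 8.97%, so the statement that it is below 10% remains true. Power at 2.5% is 78.2% rather than 81.0%, which is 2.8 points below the stated value. The statement of at least 80% power is false as written, and the claim to be as near as possible to both targets does not describe 35 patients under this rule.

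A conclusion of equivalence after at most 1 recurrence in 35 would still be valid. The figures assume independent patients with a common recurrence rate and 2-year status known for all 35. This is a correction that should be made, not a flaw that undermines the test.

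**What to change.** Restate XIII.B to D for 35 patients: cut-off 2.9% (1/35), type I error 6.6% at a true rate of 12%, power 78.2% at 2.5%. Remove the claim of 80% power, or confine it to true rates of 2.3% or less (80.8%). Reporting 78.2% at the plan's own 2.5% is the cleaner choice, since it does not pick a new alternative to recover the target. Amend the sentence in XIII.D about closeness to 10% and 80% accordingly. Add that the figures assume known 2-year local recurrence status for every patient counted. The cost is wording and a slightly less favourable stated power; the rule and the sample size stay as they are.

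If 32 evaluable of 35 enrolled was intended, say so, state the loss assumption (3 of 35, 8.6%), and write the rule's denominator as 32. Also tabulate type I error and power for 31 to 35 evaluable patients, and note that with 30 the same rule exceeds the 10% limit (11.0%). This option does change the written rule, though not enrolment.

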- iii. Toxicity from pre-operative hypofractionated radiation therapy for STS. Based on historical data, we expect there will be minimal toxicity, both acute and long-term. Adverse event rates will be compared at specific times using the CTCAE v 4.0.
- iv. Changes in imaging with MRI (T2, T1 post contrast, DCE and DWI) as well as pathologic correlation (percent necrosis, fibrosis, viable cells and tumor biomarker expression will also be ascertained in this study.
- v. Measure cytokine and tumor gene expression and immune response to radiation therapy and correlate with pathologic and clinical response.

D. Endpoint Analysis:

- i. Crude rates of locoregional recurrences will be documented as well as the time to development of recurrence or relapse. Time of last follow-up or death will also be noted. This will allow us to calculate disease-free and overall survival rates. We will compare these results to an IRB approved database that exists on pre-operative radiation therapy using standard dose and fractionation at 2 Gy per fraction to 50 Gy.
 - 1. This IRB approved database is a retrospective database in which patients with Stage I-III STS of the extremity and superficial trunk were treated with pre-operative radiation therapy using conventional fractionation. Crude rates of locoregional control, disease-free and overall survival will be assessed in this dataset.
 - 2. The data in this database is acquired from all patients who were treated with preoperative RT for localized STS from 2000-2012. This is a retrospective database of the patients treated at Froedtert and the Medical College of Wisconsin
 - 3. The variables included in this database include age, KPS, gender, cardiovascular history, smoking history, disease histology, location of disease, grade, MRI measurements, RT dose and dates, dates of surgery, pathologic findings including size, %necrosis, fibrosis and viable cells, margin status, wound complications, local recurrence, distant recurrence, survival, date of consult and last follow-up, and disease status.

XII. Statistical Considerations

- A. The PRIMARY ENDPOINT of this study is to assess local control
- B. The SECONDARY ENDPOINTS are to assess toxicity, quality of life, disease-free survival and overall survival. Also, changes in imaging (MRI) and pathologic outcomes (biomarkers, percent necrosis, fibrosis and viable cells) will also be assessed.

XIII. Power Considerations for Local Recurrence (Primary Endpoints)

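### The primary decision is stated both as a 2-year cumulative-incidence test and as a fixed count of at most 1 recurrence in 35; nothing says which governs when follow-up is incomplete, and the count's error rate exceeds 10% if enough patients are lost early

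*Combined protocol and SAP*

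**What the plan says.** - **Decision criterion (section XIII.A).** "The study will conclude equivalence if the 2-year cumulative incidence of recurrence is less than 12% at the 0.10 type I error level". The same item describes a "one-sided equivalence test with an equivalence limit of 5% and a type I error rate of 10" percent, and 12% is the sum of a 7% reference rate and the 5% limit.
- **Operating characteristics (XIII.A to D).** "Power calculations are based on exact binomial probability calculations". Items B and C give 8.97% type I error at a true rate of 12% and 81.0% power at 2.5%, both for at most 1 recurrence in 35 (printed as 3.1% or less). Item D says that a false rejection "with only 0 or 1 recurrence out of 35 patients is less than 10% if the actual recurrence rate is 12% or more", and promises at least 80% power.
- **Estimators.** XIV.A says that cumulative incidence will be calculated for local recurrence. XI.D.i says "Crude rates of locoregional recurrences will be documented", together with times to recurrence, last follow-up and death.
- **Patients who leave (section X).** Withdrawal is allowed at any point. "Subjects will not be replaced". "Follow up and data collection for withdrawn subjects will terminate at the time of withdrawal".

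Disease-free survival has a censoring rule (XI.C.i). For the primary endpoint the plan gives no censoring rule, evaluable set, dropout allowance or confidence-limit method.

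**The concern.** A cumulative-incidence estimate lets a patient leave the risk set when observation stops. A count over a fixed 35 does not: a patient who leaves at month 3 stays in the denominator and can add no later recurrence. If the count is the rule, each loss moves the trial towards concluding equivalence, and the error rate promised in XIII.D depends on a level of follow-up that the plan never states. If cumulative incidence is the rule, the error rates in XIII.B to D describe a different procedure from the one to be run. The pass mark lies between 1 and 2 events, so the choice of rule can decide the trial and should not be left until the data are known.

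**Working it through.** **Inputs from the documents:** n = 35 (X.A, XIII); null rate 12%, alternative 2.5%, one-sided level 0.10 (XIII.A); pass with at most 1 recurrence (XIII.B to D).

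**Assumptions, because the documents give no loss rate:** constant recurrence hazard over 2 years, loss unrelated to recurrence, and the range of losses shown below.

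**Step 1: the plan's own figures.** P(X ≤ 1) = (1−p)^n + n·p·(1−p)^(n−1).

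| n | at p = 12% | at p = 2.5% | 1/n |
|---|---|---|---|
| 35 | 0.0114 + 0.0544 = 6.58% | 0.4123 + 0.3700 = 78.2% | 2.9% |
| 32 | 0.0167 + 0.0730 = 8.97% | 0.4448 + 0.3649 = 81.0% | 3.1% |
| Printed for 35 | 8.97% | 81.0% | 3.1% |

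The three printed figures are not those of 35 patients; all three match 32. With 35 fully followed patients, type I error is indeed below 10%, but power is below the promised 80%.

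**Step 2: the count applied literally to 35, with m patients lost.** A patient lost after a fraction f of the 2 years shows a recurrence first with probability q = 1 − 0.88^f. Then

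P(≤ 1) = 0.88^(35−m)·(1−q)^m + (35−m)·0.12·0.88^(34−m)·(1−q)^m + m·q·(1−q)^(m−1)·0.88^(35−m).

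| Time of loss | f | q | Losses | Type I error |
|---|---|---|---|---|
| No follow-up | 0 | 0 | 4 | 9.94% |
| No follow-up | 0 | 0 | 5 | 11.0% |
| Month 3 | 0.125 | 0.0159 | 5 | 10.3% |
| Month 6 | 0.25 | 0.0315 | 5 | 9.7% |
| Month 6 | 0.25 | 0.0315 | 6 | 10.4% |
| Month 12 | 0.5 | 0.0619 | 8 | 9.9% |
| Month 12 | 0.5 | 0.0619 | 9 | 10.4% |

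With leaving times uniform over 2 years, simulation (400,000 runs) gives 9.96% for 8 losses and 10.5% for 9.

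**Step 3: exponential loss.** Let h = −ln(0.88)/2 = 0.0639 and, for 22% loss by 2 years, l = −ln(0.78)/2 = 0.1242. The chance of an observed recurrence is h/(h+l)·(1 − e^(−2(h+l))) = 0.1065, so P(≤ 1 of 35) = 10.0%. The same formula gives 9.65% at 20% loss and 11.8% at 30%.

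**Step 4: can the two rules disagree?** Take 1 recurrence and 5 patients lost with no follow-up. The count is 1 of 35 and passes. Censoring the five leaves 30 patients. The exact one-sided 90% upper limit U solves P(X ≤ 1 | 30, U) = 0.10, giving U = 12.4%, which is above 12%, so the cumulative-incidence criterion fails.

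**Step 5: do they agree with complete follow-up?** With 1 of 35 the exact upper limit is 10.7%, a pass. With 2 of 35 it is a fail, because P(X ≤ 2 | 35, 12%) = 19.2%, above 10%. They agree.

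**The case against.** The strongest reply is that section XIII concerns power. The sentence that states the conclusion is in XIII.A and names cumulative incidence, XIV.A repeats that estimator, and XI.D collects the dates needed to censor. On that reading, items B to D are an ordinary sizing simplification under complete follow-up. This is a fair reading, and it limits the point in three ways.

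- A reader might infer that the plan scores withdrawn or lost patients as recurrence-free. No section says so; it follows only if the count in XIII.D is applied literally to all 35.
- A reader might infer that any five dropouts break the 10% limit. Five suffice only if they leave by about month 3. Six are needed at month 6, and nine at month 12 or with uniform leaving times.
- A reader might take the crude rates in XI.D as a further decision rule. They are to be documented and compared with the retrospective database, and are not tied to the 12% test.

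It is also true that the documents give no loss rate, and that section VII describes the imaging follow-up as standard practice, so nothing shows that losses would reach these levels. The number 32 might reflect an allowance for 3 non-evaluable patients, but the plan does not say this.

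The reply does not settle which rule governs. XIII.D still ties rejection of the null hypothesis to 0 or 1 recurrence in 35. If XIII.A governs, its confidence-limit method is missing and the stated error rates belong to another procedure.

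**Conclusion.** The concern holds in this form: two decision criteria are stated, they agree under complete follow-up, and they can give opposite answers when patients are lost, with no text to choose between them. Under the literal count, type I error rises from 6.6% to just over 10% with 5 losses by about month 3, 6 at month 6, 9 at month 12, or about 22% exponential loss. The breach is modest near those points; with 10 patients lost without any follow-up it would be 18.0%. All of this rests on constant hazard, non-informative loss and assumed loss levels. Only withdrawal and loss to follow-up count towards it: death without local recurrence is a competing event and properly stays in the denominator.

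The mismatch in the printed figures needs no assumption about losses. For 35 fully followed patients, type I error is 6.6% and power 78.2%, so the statement of at least 80% power is wrong.

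**What to change.** Make one rule primary in section XIII: conclude only if the one-sided 90% upper confidence limit of the 2-year cumulative incidence of local recurrence is below 12%. Censor withdrawals and losses at the last local assessment, treat death without local recurrence as a competing event, and name a small-sample, exact-type limit in advance (beta-product is one option). State that the count of at most 1 in 35 is what this rule gives under complete follow-up, not a separate criterion.

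Restate XIII.B to D for the number actually used. For 35 that means 6.6% and 78.2%, with the 80% claim corrected. If 32 was meant as an evaluable number, say so and define it. Show type I error and power over a range of dropout.

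A count restricted to patients with known 2-year status is not a good substitute: it keeps every early recurrence while dropping recurrence-free leavers, which biases the rate upwards.

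The change is to the analysis text only, with no change to treatment, visits or sample size. The cost is power. If 5 patients gave no follow-up, an exact limit on the remaining 30 would allow no recurrence, and power at 2.5% would be 0.975^30 = 46.8%. Later losses contribute some information, so the loss of power should be computed for each dropout scenario and reported.
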